## DOCUMENT HISTORY

Version Number	Date of issue	Short description of change/s and cross reference to eventual protocol amendment number
2.0	08APR2016	First version signed by the Investigator (previous versions were only circulated among the Sponsor, the Investigator and the CRO). Never submitted to IRB.
3.0	14SEP2016	First version submitted to IRB
4.0	04JAN2017	
Amendment N.1
 
§1: expected study start date has been updated.
 
§5.2: inclusion criterion I6 has been modified in order to reduce the duration of PPI therapy from 3 months to 8 weeks before screening visit.
 
§6.5: clarification on the consumption of restricted foods has been added.
 
§7.2: clarification about the requirements for dating consent form has been added.
 
§10, §10.1: requirements for reporting of SAEs to FDA have been updated according to applicable regulations. Some clarifications on AEs/SAEs reporting have been added.
 
§10.2: clarifications to reporting requirements for pregnancy have been added.
 
Appendix I: corrections in the wording have been done.

5.0	15JUN2018	
Amendment N. 2
 
Expected date of last patient last visit has been extended from March 2018 to to July 2019
 
Several sections of the protocol have been modified in order to take into account the suggestions raised during the

	
Investigators' Meeting held on February 26th 2018:
 

- LT4 dose adjustments have been allowed, if TSH levels > 10 or < 0.01 mIU/L at control visits (interim or unforeseen) after inclusion.

- Reasons for withdrawal have been updated accordingly.

- LT4 dose adjustment has been added as a parameter of evaluation, secondary efficacy variable and study objective.

- Statistical analysis has been update accordingly.

- Other proton pump inhibitors (dexlansoprazole ≥ 30 mg daily and rabeprazole ≥ 20 mg daily) have been allowed.

- Use of over-the-counter PPIs has been allowed, if so directed by the prescribing doctor.

- Glucocorticoids have been allowed if at stable doses throughout the entire study duration (from screening to final visit).

- The request to interrupt intake of biotin for 2 days before the baseline (V2) and the final (V4) visits has been added.

- Information on timelines for samples shipment within 7 days from collection have been added.

 
Several sections of the protocol have been modified to take into account the revision of the Prescribing Information of Tirosint (dated 04/2017) and all levothyroxine products:
 

- Introduction on drug interactions reported for levothyroxine has been updated.

- Mode of administration of Tirosint has been updated.

- Information on the interval for serum TSH levels monitoring has been shortened from 12 to 6-8 weeks.

- Information on Pregnancy and Lactation has been updated.

- The 175 and 200 mcg strengths of Tirosint have

--	--

		
been added.
 
 
- Forbidden medications as well as precautions to be adopted with use of concomitant medications and foods have been updated.
 
 
Some inaccuracies and misspellings have been corrected throughout the text.

6.0	17JUN2019	
Amendment N. 3
 
Expected date of last patient last visit has been extended from July 2019 to April 2020.
 
Age at inclusion has been extended from 65 to 75 years (Inclusion Criterion I2).
 
The possibility to re-screen the subjects because of wash-out from forbidden medications has been deleted, as per Protocol Memo dated 04-Oct-2018.
 
Following to a revision of the Prescribing Information of Tirosint capsules (dated 06/2018):
 
 
- Reference to the Prescribing Information of Tirosint capsules has been modified from version [REDACTED] to version "IBSA Pharma Inc 2018".
 
- The distributor of Tirosint capsules has been changed from [REDACTED] to IBSA Pharma Inc, Parsippany, NJ 07054, USA.
 
- The number of capsules to be dispensed at each visit has been changed from 56 to 60; the number of capsules per blister has been changed from 7 to 10; the number of capsules per box has been changed from 28 to 30.
 
 
The signature of ICF in two originals (one for the Investigator and one for the subject) has been substituted by the signature of ICF in single copy, with original archived by the Investigator and copy given to the subject.
 
The list of documents to be retained in the ISF and TMF has been updated.

## PROTOCOL SUMMARY

Title:	An open-label therapeutic efficacy study of Tirosint® (levothyroxine sodium) capsules in thyroidectomized patients taking proton pump inhibitors.
Protocol N°:	13US/T404
Study Site(s):	Coordinating site: [REDACTED] [REDACTED] Additional sites information are provided separately.
Study Objectives:	The objective of this study is to evaluate the therapeutic efficacy of Tirosint® capsules in patients with a history of hypothyroidism and on proton pump inhibitors.
Study Population:	A maximum number of 60 (at least 48 completed) adult patients with a history of hypothyroidism due to total thyroidectomy, who are on stable doses of levothyroxine tablets (between 88 and 250 mcg daily) for at least 6 weeks before screening visit, and with a history of gastroesophageal reflux disease or associated gastrointestinal issues on prescription proton pump inhibitors (i.e. omeprazole $\geq$ 20 mg daily, or esomeprazole $\geq$ 20 mg daily, or lansoprazole $\geq$ 15 mg daily, or dexlansoprazole $\geq$ 30 mg daily, or pantoprazole $\geq$ 40 mg daily, or rabeprazole $\geq$ 20 mg daily) for at least 8 weeks before screening visit.
Study Design:	This is an open-label, phase IV study.
Treatment:	Tirosint® (levothyroxine sodium) 13, 25, 50, 75, 88, 100, 112, 125, 137, 150, 175, 200 mcg capsules [REDACTED]). The drug will be given at the same pre-study dose. Proton pump inhibitors as prescribed.
Evaluation parameters:	During the screening visit , subjects (holding their morning dose of LT4) will undergo screening serum measurements for TSH, FT4, FT3 and TT3, along with a physical examination. Subjects complying with inclusion/exclusion criteria will enter a run-in period, in which they will continue taking their levothyroxine and proton pump inhibitor medications as per prescription, at their current dose. Should the patient require LT4 dose adjustment at screening visit, it will be possible to re-screen the patient until thyroid function tests normalization under the new dose. Four to 6 weeks later, subjects (fasting and holding

their morning dose of LT4) will undergo *baseline* serum measurements of TSH, FT4, TT4, FT3, TT3, CPK, SHBG, ferritin, ACE level, and lipid panel (TG, TC, HDL, LDL, and VLDL) as baseline thyroid function related serum laboratory assessments. Patients will then be switched to Tirosint® capsules at the same daily dose. Patients will remain on Tirosint® for 12 weeks (time frame allowed: 11-13 weeks) and will continue their regular intake of proton pump inhibitor, throughout the whole study duration, according to prescription. Tirosint® will be taken as a single daily dose in the morning, on an empty stomach, one-half to one hour before breakfast. All subjects will separate their LT4 by at least 4 hours from any drug known to interfere with LT4 absorption (i.e. iron and calcium supplements, bile acid sequestrants and ion exchange resins) and by at least 1 hour from foods that are known to interfere with LT4 absorption.

Halfway through the Tirosint® treatment period (time frame allowed: 5-7 weeks), subjects will report to the clinical center and (holding their morning dose of LT4) will undergo *intermediate* serum measurements of TSH, FT4, FT3 and TT3, for safety assessment.

At the end of the 12 week Tirosint® treatment period, patients will report to the study site for the *final visit* and (fasting and holding their morning dose of LT4) they will undergo a physical examination and serum measurements of TSH, FT4, TT4, FT3, TT3, CPK, SHBG, ferritin, ACE level, and lipid panel.

In addition to the laboratory tests, the subjects' safety will be evaluated throughout the study by adverse event monitoring.

**Primary end-point:**

Change in serum levels of TSH at the end of the 12-week Tirosint® treatment period with respect to its baseline.

**Secondary end-points:**

*Efficacy assessments:*

Change in serum levels of FT4, TT4, FT3, TT3, CPK, SHBG, ferritin, ACE level, and lipid panel at the end of the 12-week Tirosint® treatment period with respect to its baseline.

Serum levels of TSH, FT4, FT3 and TT3 halfway through each treatment cycle.

LT4 dose adjustment evaluated both in terms of number of patients requiring changes in daily dose during the treatment period and as mean change in daily LT4 dose at the end of the treatment period versus the baseline.

*Safety assessments:*

Adverse events

Vital signs

Body weight

**Statistical analysis:**

*Primary Efficacy Analysis*

The primary efficacy end-point will be the change in serum levels of TSH at the end of the 12-week treatment period with Tirosint® capsules with respect to baseline.

The serum levels of TSH will be analyzed by means of a repeated measures analysis of covariance on the difference (final vs baseline visit) with basal value as covariate. The 95% confidence interval will be calculated. Additional non-parametric analyses may be performed on the evolution of TSH serum levels as sensitivity analyses.

Baseline variables (e.g. gender, pre-study LT4 product, LT4 dose, proton pump inhibitor product and dose, etc.) may also be used as covariates if appropriate.

The serum levels of TSH recorded after changes in LT4 dose will not be considered for the analysis.

*Secondary Efficacy Analyses*

The secondary efficacy end-points will be the change in

serum levels of FT4, TT4, FT3, TT3, CPK, SHBG, ferritin, ACE level, and lipid panel at the end of each 12-week treatment period with Tirosint® capsules with respect to baseline. The change in serum levels of TSH, FT4, FT3, TT3 at Visit 3 with respect to baseline will also be analyzed as secondary efficacy end-points.

Serum levels of FT4, TT4, FT3, TT3, CPK, SHBG, ferritin, ACE level, and lipid panel (TC, HDL-C, LDL-C, VLDL-C, TG) will be analyzed by means of a repeated measures analysis of covariance with basal value as covariate.

The 95% confidence interval will be calculated.

Baseline variables (e.g. gender, pre-study LT4 product, LT4 dose, proton pump inhibitor product and dose, etc.) may also be used as covariates if appropriate.

The secondary end-point parameters recorded after changes in LT4 dose will not be considered for the analysis.

The dose adjustment evaluated in terms of number of patients requiring changes in LT4 daily dose during the treatment period will be described using frequencies and percentages.

Changes in mean LT4 daily dose at the end of the treatment period versus baseline will be analyzed by means of a repeated measure analysis of variance model.

#### *Safety Analyses*

Numbers of patients experiencing Adverse Events (AEs) will be calculated. AEs will be classified using MedDRA categories. Vital signs and body weight will be analyzed by means of descriptive statistics. Moreover mean change from baseline and 95% confidence interval on mean change will also be calculated.

Expected starting date:	Expected date of first patient first visit: January 2017
Expected ending date:	Expected date of last patient last visit: April 2020

## OVERALL STUDY SCHEDULE

Visit	V1	V2	V3	V4
	Screening	Baseline	Interim	Final
Week	-4/-6	0	6±1	12±1
Period	Run-in		Treatment Period 	
Day	D-28/-42 	D1	D42 (35-49)	D84 (77-91)
Enrolment:				
Informed Consent	X			
Demographic Data	X			
Medical and Medication History	X			
Physical Exam	X 	X 		X 
Thyroid function tests	X 			
Urine pregnancy test	X	X		
Inclusion/exclusion criteria	X	X		
Inclusion		X		
Interventions:				
Levothyroxine as prescribed				
Tirosint capsules				
PPI as prescribed				
Drug dispensing		X	X	
Drug return			X	X
Outcomes:				
Thyroid function tests		X 	X 	X 
Serum lab tests 		X		X
Pill count (compliance)			X	X
AEs and concomitant medications monitoring		X	X	X

 Vital signs, height (V1 only), weight, neck exam, cardiac exam, and respiratory exam

 Weight

 TSH, FT4, FT3 and TT3 (sample to be collected pre-dose) (same tests in case of re-screening)

 TSH, FT4, TT4, FT3 and TT3 (sample to be collected pre-dose)

 CPK, SHBG, ferritin, ACE level, and lipid panel (TC, LDL-C, HDL-C, VLDL-C, and TG) (sample to be collected pre-dose and in fasting conditions)

 Day 1 of treatment period will be the first day of Tirosint® intake and should be the day of V2.

 In case re-screening is necessary, this time period may be extended, provided that time interval between re-screening and V2 is kept within -28/-42 days, and that the overall screening period does not exceed 4 months.

## LIST OF ABBREVIATIONS

ACE.....	Angiotensin Converting Enzyme
AE .....	Adverse Event
ANCOVA.....	Analysis of covariance
ANOVA .....	Analysis of Variance
BP.....	Blood Pressure
BW .....	Body Weight
CI.....	Confidence Interval
Cmax .....	Maximum plasma concentration
CPK.....	Creatine Phosphokinase
CRF .....	Case Report Form
CRO .....	Clinical Research Organisation
FT3.....	Free Triiodothyronine
FT4.....	Free Thyroxine
GERD.....	Gastroesophageal Reflux Disease
GMP .....	Good Manufacturing Practice
HDL-C .....	High-density Lipoprotein Cholesterol
HR .....	Heart Rate
IEC .....	Independent Ethical Committee
IMP.....	Investigational Medicinal Product
ITT.....	Intention to treat
IU .....	International Unit
LDL-C.....	Low-density Lipoprotein Cholesterol
LT4.....	Levothyroxine
MAH .....	Marketing Authorization Holder
MW .....	Molecular Weight
NIMP.....	Non-Investigational Medicinal Product
OTC.....	Over-The-Counter
PPI.....	Proton Pump Inhibitor
R&D.....	Research and Development
Rx.....	Prescription drug
SAE .....	Serious Adverse Event
SAP .....	Statistical Analysis Plan
SHBG.....	Sex-Hormone Binding Globulin
T3 .....	Triiodothyronine
T4 .....	Thyroxine
TBG.....	Thyroxine-Binding Globulin
TC.....	Total Cholesterol
TFT.....	Thyroid Function Test
TG .....	Triglycerides
Tmax .....	Time to achieve Cmax
TSH.....	Thyroid Stimulating Hormone
TT3.....	Total Triiodothyronine

TT4..... Total Thyroxine  
VLDL-C..... Very Low-density Lipoprotein Cholesterol  
WHO-DD..... WHO Drug Dictionary  
WIC..... Written Informed Consent

## 2 INTRODUCTION

### 2.1 Background Information

Primary hypothyroidism or thyroid hormone deficiency due to abnormality in the thyroid gland is the most common endocrine disease. The prevalence of hypothyroidism in the general population ranges from 3.8% to 4.6% ([Chakera, Pearce et al. 2012](#)).

In Western countries, the most common cause of primary hypothyroidism is autoimmune thyroiditis. However, in many parts of the world, iodine deficiency remains an important cause. Other common causes of hypothyroidism include thyroidectomy, radioiodine therapy, and drugs such as amiodarone, lithium, thionamide, iodine, interferon, sunitinib, rifampicin, and thalidomide.

Diagnosis and treatment of hypothyroidism is often considered simple and is mostly carried out in a primary care setting. However, studies continue to show problems in the management of this condition. Many patients on thyroid hormone replacement are either under-replaced or over-replaced and a significant number of patients on thyroid hormone replacement report not feeling well despite having thyroid function tests (TFTs) within the healthy reference range.

The common clinical features associated with hypothyroidism are tiredness, weight gain, dry skin, cold intolerance, constipation, muscle weakness, puffiness around the eyes, hoarse voice, and poor memory.

Overt primary hypothyroidism is diagnosed biochemically with a serum thyroid stimulating hormone (TSH) concentration above the reference range and low free thyroxine (FT4). The population reference range of TSH is around 0.4–4.5 mIU/L and most patients with overt hypothyroidism have TSH above 10 mIU/L. However, several controversies surrounding the TSH reference range have surfaced in recent years. Firstly, because the TSH in the general population is not normally distributed, and more than 95% of healthy individuals have TSH less than 2.5 mIU/L, it has been suggested that the upper limit of the TSH reference range should be lowered from 4.5 to 2.5 mIU/L ([Wartofsky and Dickey 2005](#)).

Levothyroxine (LT4) is the treatment of choice for hypothyroidism. It has a 7-day half-life, allowing daily dosing. In patients with no significant comorbidities, initiation of LT4 at a full dose based on body weight (1.6 mcg/kg/day) is usually safe and effective.

Food can interfere with the absorption and action of levothyroxine. Conventionally, hypothyroid patients are advised to take LT4 on an empty stomach at least half an hour before breakfast to prevent impairment of absorption by food.

Moreover, several medications are known to affect the level of serum thyroid hormone in patients with hypothyroidism receiving LT4 replacement, either by reducing gastrointestinal absorption of LT4 or by increasing its metabolic clearance.

Common drugs that can affect LT4 absorption include iron, calcium, bile acid sequestrants and ion exchange resins and LT4 must be taken at least 4 hours apart from these drugs. Orlistat, aluminum and magnesium hydroxides and simethicone are also known to decrease levothyroxine absorption.

Enzyme inducers, such as phenobarbital, and rifampin can increase the metabolism of levothyroxine, resulting in an increased dose requirement, while enzyme inhibitors such as beta-adrenergic agonists, glucocorticoids and amiodarone decrease the peripheral conversion of T4 to T3, leading to decreased T3 levels. Other drugs may alter the serum transport of thyroid hormones therefore requiring monitoring of thyroid hormone parameters.

Gastric acidity is an essential requirement for adequate absorption of levothyroxine. Sucralfate, antacids and proton pump inhibitors (PPIs) may cause hypochlorhydria, affect intragastric pH, and reduce levothyroxine absorption, therefore requiring appropriate monitoring of patients (IBSA Pharma Inc 2018).

PPIs are commonly used to treat conditions such as gastric and duodenal ulcers, *Helicobacter pylori* infection, and gastroesophageal reflux disease (AstraZeneca 2016).

Centanni et al. reported that omeprazole treatment was associated with an increase in the level of serum TSH in 10 patients treated with LT4, an effect that was reversed by an increase in the LT4 dose by 37% (Centanni, Gargano et al. 2006).

Similarly, Sachmechi et al demonstrated that lansoprazole affected TSH levels in patients with primary hypothyroidism receiving LT4 replacement therapy (Sachmechi, Reich et al. 2007). In the study group, 19% of the patients required an adjustment of LT4 dose after lansoprazole therapy was initiated, and the mean increase in LT4 dose was 35%.

Recently, an epidemiology study performed in the United Kingdom demonstrated significant interaction between levothyroxine and PPIs with serum TSH increasing of 0.12 mU/L and a clinically significant increase of over 5 mU/L in serum TSH presented by 5.6% of the patients (Irving, 2014). A second epidemiology study performed in Italy, also showed a significant increase of TSH levels during initial exposure to potentially interacting drugs, including PPIs, and an increased use of levothyroxine (Trifirò, Parrino et al. 2015).

The proposed mechanism for increased TSH levels during PPI therapy is a reduction in gastrointestinal absorption of LT4 due to reduction of gastric acid secretion (Centanni, Gargano et al. 2006).

## 2.2 Rationale

Tirosint (levothyroxine sodium) capsule has been proven to be bioequivalent to Synthroid tablets in healthy volunteers administered 600 mcg of LT4 in single dose (Colucci, D'Angelo et al. 2011).

A study by Pabla et al demonstrated that the *in vitro* dissolution profile of Tirosint capsule is less influenced by the pH of the medium with respect to Synthroid and a generic tablet (Pabla, Akhlaghi et al. 2009).

Following to this *in vitro* report, it has been recently demonstrated in healthy volunteers administered 600 mcg of LT4 in single dose, that absorption of LT4 is less influenced by i.v. infusion of 80 mg esomeprazole when administered in the form of Tirosint capsule than of Synthroid tablet (Seng Yue et al, 2015).

This pilot study is aimed at assessing whether the *in vitro* and *in vivo* reports are confirmed in the clinical setting of hypothyroid patients.

### **2.3 Potential risks and benefits**

In this study the patients will continue their therapy with LT4 and with PPIs at the prescribed doses, therefore no safety concern is advised.

The risk of switching from one LT4 formulation to another is minimized by the check of TFTs after 6 and 12 weeks from the switch, as recommended in clinical practice.

Should the hypothesis be demonstrated, the patients may benefit from a better controlled serum TSH. The study may benefit the overall population in the future.

## **3 TRIAL OBJECTIVES**

### **3.1 Primary objective (s)**

The primary objective of this study is to evaluate the therapeutic efficacy of Tirosint capsules in patients with a history of hypothyroidism and on PPIs.

The hypothesis is that PPIs may have less of an effect on the absorption, as assessed by alteration in serum TSH, of Tirosint capsules when compared to standard tablets therapy in this patients population.

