#### *Study design and study population*

The study has been designed as a preliminary evaluation in patients, therefore an open-label, non-randomized design has been judged appropriate.

Each patient's control will be the baseline evaluation with their standard therapy.

Thyroidectomized patients have been selected being the endogenous production of thyroid hormones absent; therefore, circulating thyroxine (T4) is of exogenous origin only.

Patients with GERD or associated gastrointestinal issues have been selected as these are common pathologies, which are usually treated with PPIs.

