## 5.2 Inclusion criteria

Inclusion in the study requires compliance with all the following criteria for inclusion:

- I1. written informed consent duly read, signed and dated by the subject;
- I2. aged  $\geq 18$  and  $\leq 75$  years;
- I3. history of hypothyroidism due to total thyroidectomy;
- I4. on stable LT4 tablet doses for at least 6 weeks at screening ( $\geq 88$  mcg daily and  $\leq 250$  mcg daily);
- I5. TSH at screening  $\geq 0.3$  and  $\leq 4.0$  mIU/L;
- I6. history of gastroesophageal reflux disease or associated gastrointestinal issues on prescription PPIs (i.e. omeprazole  $\geq 20$  mg daily, or esomeprazole  $\geq 20$  mg daily, or lansoprazole  $\geq 15$  mg daily, or dexlansoprazole  $\geq 30$  mg daily, or pantoprazole  $\geq 40$  mg daily, or rabeprazole  $\geq 20$  mg daily) for at least 8 weeks before screening visit and for whom chronic therapy with PPIs for the next 5 months has been prescribed;
- I7. for women, adequate and continuative contraceptive measures until the end of the study, if not in menopause;
- I8. reasonable assumption of understanding the study and willingness to take part to the study and to comply with protocol requirements.

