## **6.7 Treatment allocation and randomisation procedures**

The study is a non-randomized study.

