#### 3.2 HYPOTHESES TO BE TESTED

##### Primary objective

The primary objective of this study is to evaluate the therapeutic efficacy of Tirosint® capsules in patients with a history of hypothyroidism and on PPIs.

The hypothesis is that PPIs may have less of an effect on the absorption, as assessed by alteration in serum TSH, of Tirosint® capsules when compared to standard tablets therapy in this patients' population.

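### The stated hypothesis is that PPIs affect capsules less than tablets, but every patient is on a PPI throughout, so the TSH contrast tests only the same-dose switch in PPI users

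*Protocol*

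**What the plan says.** Protocol 3.1 gives the primary objective as the efficacy of Tirosint in hypothyroid patients on PPIs, then adds: "The hypothesis is that PPIs may have less of an effect on the absorption, as assessed by alteration in serum TSH, of Tirosint capsules", set against tablets. SAP 3.2, the section on hypotheses to be tested, repeats the comparison ("capsules when compared to standard tablets therapy in this patients").

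The design is described as follows:

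- The Protocol Summary gives the primary end-point as "Change in serum levels of TSH at the end of the 12-week Tirosint® treatment period with respect to its baseline".
- Protocol section 4 (study design and study population) names the comparator: "Each patient's control will be the baseline evaluation with their standard therapy".
- Protocol 6.7 says "The study is a non-randomized study".
- Inclusion criterion I6 requires PPI use "for at least 8 weeks before screening visit and for whom chronic therapy with PPIs for the next 5 months has been prescribed".
- Protocol 6.2 keeps patients on the PPI during the tablet run-in and during capsule treatment. A patient whose PPI is interrupted leaves the study.
- SAP 9.4.1 tests mean TSH at Visit 4 against baseline.

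As background, Protocol 2.2 says the capsule has been "proven to be bioequivalent to Synthroid tablets in healthy volunteers administered 600 mcg of LT4 in single dose".

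**The concern.** To say that PPIs affect one formulation less than the other is to compare two PPI effects. Each of those effects is a difference between TSH with and without a PPI. The trial observes neither formulation without a PPI, so it observes neither effect.

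The tablet baseline does not reveal the PPI effect on tablets either. Patients enter with a screening TSH of 0.3 to 4.0 mIU/L (I5), and the tablet dose may be adjusted and the patient re-screened until TSH is normal (Protocol 7.2). The baseline therefore reflects a dose already settled while the patient was on a PPI.

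What is at stake is the conclusion. Protocol 2.2 presents the study as a clinical confirmation of laboratory and healthy-volunteer findings on pH and PPIs, and Protocol 2.3 speaks of the hypothesis being demonstrated. Read that way, a significant fall in TSH would be taken as evidence for a mechanism, although a general difference between products or a drift over time would give the same result.

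**Working it through.** **1. The plan's own figure.** Protocol 11.3.1 gives a target difference of 0.7, an SD of differences of 1.9, 48 subjects, 70% power and a two-sided 0.05 paired t-test.

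- Noncentrality = (0.7/1.9) × √48 = 2.55. The exact noncentral t with 47 df gives power 70.5%, and 48 is the smallest number that reaches 70%.
- Maximum enrolment: 48/(1 − 0.20) = 60.
- With the 45 completers in SAP 4.1, power is 67.6%.

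The sample-size statement is correct for the contrast that will be tested.

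**2. What the contrast contains.** Let T0 and C0 be mean TSH on tablets and capsules without a PPI, T1 and C1 the same with a PPI, and δ any time or participation effect. The observed change is

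D = C1 − T1 + δ = (C0 − T0) + [(C1 − C0) − (T1 − T0)] + δ.

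The hypothesis concerns the square bracket. The trial estimates D alone, because T0 and C0 are never observed and δ has no concurrent tablet group to measure it. Suppose D = −0.7. Illustrative splits that fit it equally well are:

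| PPI-specific part | Everything else | Total |
|---|---|---|
| −0.70 | 0 | −0.70 |
| 0 | −0.70 | −0.70 |
| +0.35 | −1.05 | −0.70 |

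The PPI-specific part can be zero or of either sign.

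**3. Precision of the total.** With 45 pairs and SD 1.9, the 95% half-width = t(0.975, 44) × 1.9/√45 = 2.015 × 0.283 = 0.571 mIU/L. This describes D. It says nothing about the bracket.

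**4. What a significant result would show.** Set the PPI-specific part to zero and let the rest shift mean TSH by an assumed amount (the first two shift sizes are not from the documents; 0.7 is the plan's target). The probability of p < 0.05 is:

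| Assumed shift (mIU/L) | 45 pairs | 48 pairs |
|---|---|---|
| 0.35 | 23% | 24% |
| 0.5 | 41% | 43% |
| 0.7 | 68% | 71% |

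The test responds to the size of the change and cannot indicate its source.

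**5. Scale of a direct test (illustration only).** Comparing TSH change between PPI users and non-users, with SD 1.9 in each group and all of the 0.7 PPI-specific, takes 2 × (1.960 + 0.524)² × (1.9/0.7)² = 90.9, so 91 per group (182 in all) for 70% power. The stated hypothesis is a different and larger question than the one the trial was sized for.

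**The case against.** The first sentence of the objective fits the design, the endpoint and the SAP test are stated plainly, and the hypothesis is hedged. The study is called a pilot and a preliminary evaluation. Protocol 2.2 also cites more than bioequivalence: it reports a healthy-volunteer study in which esomeprazole influenced absorption less for the capsule than for the tablet, and in vitro data against a brand and a generic tablet. On this view the mechanism comes from earlier work, and the trial asks whether a matching change appears in patients. The run-in, with its diary, also puts patients under study conditions on tablets before baseline, which may absorb some participation effect.

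Much of this stands. A reader might infer that the trial can say nothing at all about PPIs, or that it needed a control arm. The documents do not support either. An indirect inference is available, and a preliminary study may reasonably use each patient as their own control. But the inference needs equivalence without a PPI and no time effect, and neither document states these as assumptions of the analysis. The equivalence evidence is a single 600 mcg dose in healthy volunteers against one brand, whereas I4 admits patients on LT4 tablets without naming a product. The pilot label does not turn the contrast into a test of the hypothesis listed for testing.

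A reader might also count it as an error that SAP 9.4.1 leaves out PPI and pre-study tablet product as covariates. Protocol 11.3.6 made them optional, and with every patient on a PPI they could not supply the PPI-free state.

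**Conclusion.** Wrong as written. Protocol 3.1 and SAP 3.2 name a difference in PPI effect between formulations, and the planned analysis estimates the change after a same-dose switch in PPI users plus any time or participation effect. The mismatch follows from the design and needs no numerical assumption.

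The ±0.57 mIU/L for the total assumes the planned SD of 1.9, an unadjusted paired analysis on the original scale, and all 45 completers contributing a pair. SAP 8 excludes values recorded after LT4 dose changes, so fewer may contribute observed pairs.

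It is tempting to describe the PPI-specific part as some share between none and all of the observed change. That is not supported: the components can oppose each other and the time effect is a third unknown, so no such bounds apply. Nor does the point touch the sample size, the endpoint or the model, all of which serve the narrower question. How the results will be reported is not known from these documents. The risk lies in the wording of Protocol 2.2, 2.3 and 3.1 and SAP 3.2.

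**What to change.** In SAP 3.2, by a dated revision or a note in the statistical report (SAP section 1 already provides for explaining deviations there), and in the conclusions of the study report, state the tested hypothesis as: *in thyroidectomized patients on continuous PPI therapy, mean serum TSH changes from baseline on LT4 tablets to week 12 on Tirosint at the same dose*.

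Add that a PPI-specific effect is not tested, and that any such inference is indirect and depends on no time effect and on capsule-tablet equivalence without a PPI.

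The protocol need not be rewritten, since SAP 4.1 shows the trial has ended. A table of TSH change by PPI and by pre-study tablet product, both recorded in the CRF, is optional. It would be descriptive only, because it has no PPI-free cell.

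The cost is a few sentences and a more modest claim. No patients, analyses or sample-size figures change.
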